### Sensitivity Analyses

1. **Per-Protocol and As-Treated Analysis.** The extent of non-adherence to protocol will be described by arm. Cumulative event plots will be used to compare non-adherence to protocol (as a binary event) by arm. If there is a substantial difference in non-adherence

across treatment arms, we will adjust for non-adherence in the secondary analyses of the primary endpoint

2. The  $\text{FiO}_2/\text{SpO}_2$  ratio will be normalized for altitude above sea level (atmospheric pressure) using standard equations.
3. **Incomplete Data** While missing data is an inevitable problem in longitudinal studies, we will make every possible effort to ensure final assessments for all participants, including those opting to discontinue study participation. Possible mechanisms for missingness-missing completely at random (MCAR), missing at random (MAR), nonignorable or not missing at random (NMAR)-will be evaluated prior to implementing methodology intended to minimize bias from missing data. We anticipate that <5% of randomized subjects will have missing data in the components required to compute the study outcomes. Imputation is not commonly used for rank-based statistical methods such as the van Elteren or Wilcoxon Rank-sum test. If the missingness rate exceeds 5%, we will carry out a sensitivity analysis of the primary outcome using linear regression with multiple imputation. The primary analysis will be a complete case analysis.

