## **2.7. Participant withdrawal / Early termination**

Participants may voluntarily withdraw from the study at any time and for any reason. The reason for study discontinuation will be recorded on the source documents and in all such participants, we will document: (1) vital signs (inpatients only); (2) compliance with the treatment; (3) adverse effects. (4) specific reason for withdrawal if possible; (5) functional status and symptoms (including the dyspnea Borg scale).

The study medication will be discontinued if any of the following occur at any time: (1) acute kidney injury with eGFR<30 ml/m^2/min; (2) Suspected or confirmed rhabdomyolysis; (3) Red or brown urine, which may indicate myoglobinuria, unless considered by the investigator to be clearly not due to rhabdomyolysis (for instance, in the presence of normal circulating creatine kinase); (4) Liver failure or increased AST or ALT to >3 times the upper limit of normal. In cases in which the medication is discontinued, data collection will continue normally as per the usual study protocol.

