For non-normal distributed continuous outcomes, we will utilize non-parametric methods or consider distribution-stabilizing transformations. Levine's tests will be used to assess homogeneity of variance. The models will include data from dropouts. Model assumptions will be examined (eg, QQ plots to assess normally distributed residuals for valid Wald tests).

All-cause death will be evaluated using Cox proportional hazards models. The proportional hazards assumption will be assessed via weighted versions of Kaplan-Meier curves, using log-log plots and graphical displays based on the Schoenfeld and scaled Schoenfeld residuals, and violations of the proportional hazards assumption will be addressed with a time-interaction term.

We will make every possible effort to minimize missing data and ensure final assessments for participants opting to discontinue study participation. Missing data, however, is an inevitable problem in a longitudinal study. The mechanism for missingness-missing completely at random (MCAR), missing at random (MAR), nonignorable or not missing at random (NMAR)-will be evaluated prior to implementing methodology intended to minimize bias from missing data. We anticipate that <5% of randomized subjects will have missing data in the components required to compute the study outcomes. Imputation procedures will be applied as needed for missing data, and the primary analyses will use the imputed data.

The intent-to-treat principle of including all randomized participants in the outcome models will be followed. Analytic methods described above will take advantage of all available data. Sensitivity analyses will be performed including only participants with laboratory confirmation of COVID-19 and using an 'as-treated' analysis. The 'as-treated' analysis will take into account subjects in the control arm who begin fenofibrate as part of their clinical care, and those in the fenofibrate arm who stop using fenofibrate for any reason. We will also perform sensitivity analyses in which the  $\text{FiO}_2/\text{SpO}_2$  ratio will be theoretically normalized for altitude above sea level (atmospheric pressure).

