## ANALYSIS

**Intention to Treat Principle** Unless otherwise specified, all analyses are conducted on an 'as-randomized' basis, irrespective of adherence to treatment. This analysis follows the intention to treat principle pre-specified in the protocol.

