### Descriptive Statistics (Intention to treat cohort)

Analyses will be for the overall cohort, stratified by arm and stratified by in/out patient status at randomization. The outcomes and baseline characteristics of the subjects will be described using proportions for categorical variables and means/medians as well as standard deviations (SD) and interquartile range (IQR) for continuous variables.

**Primary Analysis:** This analysis will use a two-sided van Elteren test, the stratified version of the Wilcoxon rank sum test. For each stratum, estimation, and 95% confidence intervals of differences between arms will use both the Hodges-Lehman median difference and the Mann-Whitney Parameter, the probability that a subject from the treatment arm has a score greater or equal to that of a subject for the control. In addition to the primary outcome, the Wilcoxon test will be used to test hypotheses involving the continuous secondary and exploratory outcomes.

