### Regression models

Linear regression analysis to estimate the treatment effect for each continuous outcome of interest will adjust for covariates including age, sex, inpatient vs. outpatient status at enrollment, FiO2/SpO2 at the time of enrollment, ethnicity, body mass index, altitude above sea level and history of diabetes at baseline. Although not specified in the initial protocol, at the recommendation of the DSMB, we will add Country as a fixed effect with the goal of adjusting for a broad indicator of treatment practices, timing of variants, and timing of surges. We will also perform sensitivity analyses clustered study site.

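### A secondary analysis of the primary endpoint would adjust for post-randomisation non-adherence when the arms differ, which biases the arm effect if stopping is related to outcome

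*SAP*

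**What the plan says.** The SAP's default is that "all analyses are conducted on an 'as-randomized' basis, irrespective of adherence to treatment". The primary analysis follows it: "This analysis will use a two-sided van Elteren test, the stratified version of the Wilcoxon rank sum test", with no adherence term.

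Sensitivity Analyses, item 1 (Per-Protocol and As-Treated Analysis) departs from the default. Non-adherence is first described: "Cumulative event plots will be used to compare non-adherence to protocol (as a binary event) by arm". A conditional rule follows. "If there is a substantial difference in non-adherence" is seen across arms, then "we will adjust for non-adherence in the secondary analyses of the primary endpoint". No threshold for substantial, no adjustment method and no estimand is given, and non-adherence itself is not defined.

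The nearest guide to method is the Regression models section, which follows the Secondary Analysis heading: "Linear regression analysis to estimate the treatment effect for each continuous outcome of interest will adjust for covariates including age, sex", and further characteristics recorded at enrolment, with country added. Non-adherence is not in that list.

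Protocol section 7.2 has a related but different plan, with no trigger: "Sensitivity analyses will be performed including only participants with laboratory confirmation of COVID-19 and using an 'as-treated' analysis".

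On why participants stop, Protocol section 2.7 begins "The study medication will be discontinued if any of the following occur at any time" and lists acute kidney injury, suspected or confirmed rhabdomyolysis, discoloured urine, and liver failure or raised transaminases. Section 8.2 says fenofibrate can raise transaminases and creatinine. Section 4.3 lists worsening renal and liver function among the events expected from COVID-19 itself.

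**The concern.** Randomisation makes the arms comparable at baseline. A variable that develops later and responds to both the drug and the illness does not share that protection. Here the same stopping criteria can be reached through a drug effect or through deterioration, and deterioration also drives the global rank. A participant who stopped on placebo and one who stopped on fenofibrate may therefore differ in severity, and so may those who continued. Conditioning on stopping compares unlike groups.

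At stake is a prespecified secondary analysis of the primary endpoint. Suppose more participants stop on fenofibrate and those who stop tend to be sicker. The adjustment then credits part of the stoppers' poor outcomes to stopping rather than to chance or illness, and the arm coefficient shows a benefit even when the drug does nothing. If more stop on placebo, the error runs the other way. A reader who sees this result beside the as-randomised one has no way to tell bias from effect.

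**Working it through.** The plan states no figure that could be reproduced, so the check is algebra followed by simulation under no treatment effect.

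**Inputs from the documents.** 700 participants (Protocol 2.3), allocated 1:1 (2.5), so 350 per arm; non-adherence as a binary variable (SAP, Sensitivity Analyses).

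**Assumed, because the documents are silent.** The stopping rates, and how strongly stopping depends on severity.

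**Algebra.** Fit rank = b0 + b_A × arm + b_M × non-adherent by least squares, with higher rank better. Then

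adjusted arm effect = as-randomised difference − b_M × (rate on fenofibrate − rate on placebo).

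If sicker participants stop, b_M is negative. If more stop on fenofibrate, the bracket is positive, so the adjusted effect is shifted in favour of fenofibrate. The shift disappears if the rates are equal or if b_M is zero.

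**Simulation, moderate severity link.** Severity is standard normal. Outcome is minus (severity + noise), ranked 1 to 700. Stopping is logistic in severity with slope 0.8 or 1.2. There were 2,000 replicates per setting, tested at two-sided 0.05.

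| Stopping, fenofibrate vs placebo | Bias in adjusted arm effect (ranks) | Type I error |
|---|---|---|
| 5% vs 5% | about 0 | 5–6% |
| 7% vs 5% | 2–3 | 4–6% |
| 10% vs 5% | 5–7 | 6–8% |
| 15% vs 5% | 11–14 | 11–16% |

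The as-randomised analysis stayed within about 1 rank of zero, with type I error of 5–6%.

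The table agrees with the algebra. A bias of 11 to 14 ranks at a 10-point difference implies b_M of −110 to −140. That predicts 0.05 × 110 to 140 = 5.5 to 7 ranks at 10% versus 5%, and 0.02 × 110 to 140 = 2.2 to 2.8 ranks at 7% versus 5%.

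**Stronger severity link.** Here stopping occurs when a latent variable correlated 0.8 with severity crosses a threshold. The bias at 10% versus 5% is 1.55 rank points out of 100, or 1.55 × 7 = 10.9 ranks of 700 (type I error 0.11). At 15% versus 5% it is 2.97 × 7 = 20.8 ranks (0.29).

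**Stopping unrelated to outcome.** At 15% or 25% versus 5%, bias is about 0 and type I error 0.05.

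**Baseline adjustment.** If baseline covariates capture half of severity (an assumption), the 15% versus 5% bias falls to about 5 to 7 ranks and type I error to about 7%. If the extra stopping is also unrelated to severity, bias is 3 to 4 ranks and type I error 5–6%.

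**Scale.** For an untied rank-sum test at the protocol's final alpha of 0.0492 and 80% power, the detectable mean-rank difference is (1.967 + 0.842) × √(701 / (12 × 350 × 350)) × 700 = 42.9 ranks. This is a yardstick only; the protocol states its target as a difference in median ranks.

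**The case against.** The best defence is that this is one item in a list of sensitivity analyses. The primary test is as randomised, so confirmatory type I error is untouched. That stands.

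The second defence concerns size. The documents give no stopping rates, and section 8.2 says periodic laboratory monitoring does not apply to a 10-day course, so some laboratory-driven stopping would go unseen. The SAP regression also adjusts for age, inpatient status and baseline oxygenation, which absorbs some severity. This stands too: with small excess stopping or good baseline adjustment, the bias is only a few ranks.

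Third, the protocol already planned an as-treated analysis, so adherence is a legitimate subject. It is, but interest in adherence does not justify adjusting for it as if it were a baseline variable.

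Some stronger readings should be resisted. A reader might infer that the primary result is compromised; it is not. A reader might infer that a difference between arms is the only case in which adjustment biases the result. That is true only of a single additive covariate. The SAP names no method, and its heading mentions per-protocol analysis. Excluding non-adherers gave bias of 3.2 to 13.8 rank points out of 100 at equal rates (5% to 25% in each arm) when sicker participants stopped on fenofibrate and healthier ones on placebo. Nor is an arm difference sufficient, since bias also needs stopping to relate to outcome. Finally, nothing in the documents shows that the sponsor would rely on this analysis for its conclusions.

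**Conclusion.** The point holds for the secondary analysis. The SAP commits, on an undefined trigger, to conditioning on a variable that the protocol itself indicates can follow both treatment and illness. Under covariate adjustment, the resulting arm effect does not estimate the as-randomised effect whenever the rates differ and stopping relates to outcome. It favours fenofibrate if sicker participants stop and more of them are on drug.

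The size is illustrative: 2 to 3 ranks at 7% versus 5%, 5 to 7 at 10% versus 5%, and 11 to 14 at 15% versus 5% (type I error 11 to 16%). The figures are larger if stopping tracks severity more closely, and the 15% versus 5% figures roughly halve with informative baseline covariates. All rest on assumed stopping rates and an assumed severity link. The direction and mechanism rest on the documents. The change should be made, but the trial's main inference does not depend on it.

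**What to change.** Delete the conditional adjustment for non-adherence. Keep the descriptive summaries and plots of adherence by arm, and keep the as-randomised analysis as the estimate of effect. Protocol 2.7 continues data collection after study drug is stopped, so the outcomes needed are available.

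If the effect of taking the drug is wanted, prespecify a complier-average estimate as follows:

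- Use randomised arm as the instrument and actual fenofibrate exposure as treatment received: zero on placebo unless open-label fenofibrate is used.
- Define exposure exactly, including how deaths before day 10 count.
- State the exclusion restriction, namely that assignment affects outcome only through fenofibrate exposure.
- Label the result supportive and report it whatever the adherence difference.

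Exposure must not be defined as the share of assigned capsules taken in each arm. In a placebo-controlled trial that share is nearly the same in both arms, which leaves almost no first stage. In simulation the 5th to 95th percentile range of the estimate was wider than ±500 ranks even at 15% versus 5% stopping. With fenofibrate exposure the estimate is well behaved. For example, if 15% of the fenofibrate arm took none and nobody on placebo took any, it equals the as-randomised difference divided by 0.85, or 1.18 times that difference.

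The cost is a few lines of SAP wording, one extra analysis and a slightly wider interval for that estimate. Trial conduct does not change.

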### Subgroup analyses

Exploratory subgroup analyses will follow the plans described above with emphasis on estimation and confidence intervals for the purpose of hypothesis generation in future studies. Subgroups include

1. Sex
2. Age (categorized by < or  $\geq$  the median value in the study population),
3. Race
4. Diagnosis of diabetes at randomization,
5. Body mass index (categorized by obese or non-obese)
6. Inpatient vs. outpatient status at the time of enrollment,
7.  $\text{FiO}_2/\text{SpO}_2$  at the time of enrollment (categorized by < or  $\geq$  the median value in the study population)
8. Duration of symptoms prior to randomization (<7d vs.  $\geq$ 7 days) and
9. Fasting triglyceride levels (when available, categorized by < or  $\geq$  the standard median value).
10. Country
11. Baseline disease severity (low, medium, high based on WHO criteria) \*
12. Enrollment epoch/period (will divide into 3 epochs, early, mid, late)
13. Fenofibrate formulation (fenofibrate nanoparticle formulation (used in the USA, Lebanon and Greece), fenofibrate micronized formulation (used in Peru and Mexico) or fenofibric acid (used in Colombia). We will also do a stratified analysis of all fenofibrate formulations vs. fenofibric acid. Although all preparations utilized are approximately dose-equivalent, these analyses are pre-specified due to potential pharmacokinetic differences between the formulations, as well as recent data suggesting that there may be differential potency of fenofibrate as opposed to fenofibric acid *in vitro*, at least in some viral strains and/or culture systems. We note, however, that potential *in vitro* differences between fenofibrate and fenofibric acid are likely much less relevant *in vivo*, since fenofibric acid is the active metabolite of fenofibrate.

Country, Baseline Disease Severity, and Enrollment epoch/period were recommended as subgroups by our DSMB and prior to conclusion of enrollment. Their recommendation acknowledged variation in standard of care among different countries as well as subgroups that

were pre-defined prior to initiation of the study. Fenofibrate formulation was also added as a subgroup analysis due to the use of 3 different formulations depending on availability within a given country. We will also visually explore trends of epoch by country, plotting study month at enrollment versus summary statistics of the primary outcome by treatment and country.

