## SUMMARY AND TRIAL OVERVIEW

The severe acute respiratory syndrome coronavirus 2 (SARS-CoV-2), the virus responsible for coronavirus disease 2019 (COVID-19), is associated with a high incidence of acute respiratory distress syndrome (ARDS) and death. Aging, obesity, diabetes, hypertension and other risk factors associated with abnormal lipid and carbohydrate metabolism are risk factors for death in COVID-19.

Recent studies suggest that COVID-19 progression is dependent on metabolic mechanisms. Moreover, gene expression analyses in cultured human bronchial cells infected with SARS-CoV-2 and lung tissue from patients with COVID-19, indicated a marked shift in cellular metabolism, with excessive intracellular lipid generation. In this cell culture system, fenofibrate (a widely available low-cost generic drug approved by the FDA and multiple other regulatory agencies around the world to treat dyslipidemias) at concentrations that can be achieved clinically, markedly inhibited SARS-CoV-2 viral replication. Fenofibrate also has immunomodulatory effects that may be beneficial in the setting of COVID-19. The aim of this trial is to assess the clinical impact of fenofibrate (administered for 10 days) to improve clinical outcomes in patients with COVID-19.

The **primary endpoint** of the trial will be a global rank score that ranks patient outcomes according to 5 factors: (1) time to death (ranked from shortest to longest, up to 30 days post-randomization), (2) the number of days supported by mechanical ventilation (invasive or non-invasive) or extracorporeal membrane oxygenation (until hospital discharge, up to 30 days post-randomization, ranked from longest to shortest); (3) The inspired concentration of oxygen/percent oxygen saturation ( $\text{FiO}_2/\text{SpO}_2$ ) ratio area under the curve (until hospital discharge, up to 30 days post-randomization, ranked from highest to lowest); (4) For participants enrolled as outpatients who are subsequently hospitalized, the number of days out of the hospital during the 30 day-period following randomization (ranked from lowest to highest); (5) For participants enrolled as outpatients who don't get hospitalized during the 30-day observation period, the modified Borg dyspnea scale (mean value of assessments at ~5, and ~10 and ~15 days).

**Secondary endpoints** will include:

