#### Inclusion Criteria

- (1) Age 18 years or older
- (2) A diagnosis of COVID-19, based on: (a) A compatible clinical presentation with a positive laboratory test for SARS-CoV-2, or (b) Considered by the primary team to be a Person Under Investigation undergoing testing for COVID-19 with a high clinical probability, in addition to

- compatible pulmonary infiltrates on chest x-ray (bilateral, interstitial or ground glass opacities) or chest CT.
- (3) Able to provide informed consent.
- (4) Fewer than 14 days since symptom onset.

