### **7.3. Subgroup analyses and effect modification**

We will assess for effect modification and exploratory subgroup analyses will be performed according to sex, age (categorized by < or  $\geq$  the median value in the study population), race, presence of pre-existing diabetes, body mass index (categorized by obese or non-obese), inpatient vs. outpatient status at the time of enrollment,  $\text{FiO}_2/\text{SpO}_2$  at the time of enrollment (categorized by < or  $\geq$  the median value in the study population), duration of symptoms prior to randomization (<7d vs.  $\geq$ 7 days) and fasting triglyceride levels (when available, categorized by < or  $\geq$  the standard median value).

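### Five continuous effect modifiers are examined only as two-way cuts, so the exploratory effect-modification estimates are less precise than the data allow

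*SAP*

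**What the plan says.** SAP Subgroup analyses lists five modifiers that are measured or counted on a scale, and reduces each to two groups:

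- Age (item 2, "Age (categorized by < or" at least the cut) and baseline FiO2/SpO2 (item 7) are cut at "the median value in the study population".
- BMI (item 5) is cut at obesity: "Body mass index (categorized by obese or non-obese".
- Symptom duration (item 8) is cut at one week: "Duration of symptoms prior to randomization (<7d vs" seven days or more.
- Triglycerides (item 9) begin "Fasting triglyceride levels (when available, categorized by < or" and refer to a median whose value and source are not given.

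Protocol 7.3 uses the same cuts, for instance "body mass index (categorized by obese or non-obese". It also says that effect modification will be assessed, but names no model. SAP Regression models lists age, BMI and FiO2/SpO2 as adjustment covariates, with no interaction with treatment; their scale is not stated, although no cut is mentioned there. The SAP describes the subgroup work as exploratory, centred on estimates and confidence intervals, and intended to generate hypotheses. No power is claimed for it.

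**The concern.** The purpose of these analyses is to suggest who may benefit more or less, and the product is an estimate with an interval. Cutting a scale in two discards the differences between patients on the same side of the cut. If benefit changes gradually with the modifier, the estimate of that change is then less precise than the same data permit. The result also depends on where the cut falls. The medians for age and FiO2/SpO2 are unknown until the data are in, and another trial with different medians could not reproduce the same groups.

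This is separate from whether the two subgroup effects are formally compared. A contrast computed on the cut variable carries the same loss.

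**Working it through.** **The plan's own figure.** Neither document states a power for effect modification, so there is none to reproduce. As a check on the arithmetic, Protocol 7.1 gives 90% power for 1.7 days with N = 700 and SD 7; a two-sample calculation gives 89.5%, which agrees.

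**Inputs.** From the documents: N = 700 and outcome SD of 7 or 14 days (Protocol 7.1), 1:1 allocation (Protocol 2.5), and symptom duration of 0 to 13 days (Inclusion Criteria, "Fewer than 14 days since symptom onset"). Assumed: the modifier distributions, the share of obese patients, a linear gradient, two-sided alpha 0.05, and 80% as the reference power on the full scale.

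**Information kept.** For a linear treatment-by-modifier effect, this is the squared correlation between the modifier and its two-group indicator. For a normal modifier with a proportion p above the cut, it is phi(z_p)^2 / [p(1-p)]; at the median this is 2/pi. For symptom duration uniform over the whole days 0 to 13 and cut at 7, p = 0.5, the group means differ by 7 and the variance is (14^2 - 1)/12 = 16.25. The information kept is 0.25 x 49 / 16.25 = 0.754, close to the 0.75 of a continuous uniform variable cut at its middle.

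**Power after the cut** = Phi(2.80 x sqrt(kept) - 1.96), where 2.80 = 1.96 + 0.84.

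| Assumed modifier and cut | Kept | Lost | Power (80% uncut) |
|---|---|---|---|
| Uniform, mid-range | 0.75 | 25% | 0.68 |
| Normal, median | 0.637 | 36% | 0.608 |
| Normal, 35% above (obese) | 0.603 | 40% | 0.585 |
| Normal, 25% above (obese) | 0.539 | 46% | 0.538 |

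Simulation with N = 700, a ranked outcome and 4,000 runs gave, for continuous versus cut, 81% vs 69% (uniform, median), 79% vs 59% (normal, median) and 80% vs 57% (normal, 35% above).

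**Sensitivity.** If symptom duration is bell-shaped over 0 to 13 days, the 7-day cut loses 34-37% (power 60-63%). If a log-normal modifier acts linearly on its raw scale, a median cut loses 41%, 48% and 58% at log-SD 0.3, 0.5 and 0.7.

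**Detectable gradient, ICU- and ventilator-free days, 80% power.**

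- Full scale: 2.80 x 2 x SD / sqrt(700). With SD 7 this is 39.2 / 26.46 = 1.48 days per SD of the modifier; with SD 14 it is 2.96.
- Median cut of a normal modifier: the difference between two subgroup effects has standard error 4 x SD / sqrt(700), and the halves lie 1.596 SD apart. With SD 7, 2.80 x 28 / 26.46 / 1.596 = 1.86; with SD 14, 3.71.
- Ratio: 1.86 / 1.48 = 1.25, whatever the outcome SD.

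Triglycerides are used only where available, so their N is below 700 and both detectable gradients are larger.

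**The case against.** The best defence is that the plan contains no error here. The analyses are labelled exploratory, claim no power and support no confirmatory conclusion, and the SAP carries the protocol's cuts forward unchanged. The cuts also suit the plan's estimators: the Hodges-Lehmann difference and the Mann-Whitney parameter compare two arms within a group. A regression slope on the global rank score is a different quantity. All of this stands. It makes the point an optional improvement and limits where the slope is easily read, but it does not remove the loss of precision in analyses whose stated aim is estimation.

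A second objection is that power is modest either way. The full-scale gradient detectable with 80% power, 1.48 days per SD at outcome SD 7, equals the whole main effect detectable with 80% power: 2.80 x 7 x sqrt(2/350) = 1.48. For a gradient half that size, power is about 29% uncut and 20% cut. This is correct, and it is why the result is best judged by interval width rather than by power.

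A reader might infer two stronger things that the documents do not support:

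- That the trial's planned 80% power is eroded. That figure in Protocol 7.1 belongs to the primary treatment comparison and is untouched; the 80% used here is only a reference.
- That the trial's rationale predicts a graded benefit. The protocol summary says that "risk factors associated with abnormal lipid and carbohydrate metabolism are risk factors for death in COVID-19", which is a statement about prognosis. A gradient in fenofibrate's effect is plausible, but it is an inference.

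**Conclusion.** The point holds as a low-cost improvement. As written, the only named analyses of effect modification for these five variables use two-way cuts. Under a roughly linear gradient, the four assumed cases lose 25% to 46% of the information and lower a reference power of 80% to about 54-68%. For ICU- and ventilator-free days, the detectable gradient rises by about 25% under a median cut: 1.5 to 1.9 days per SD of the modifier at outcome SD 7, or 3.0 to 3.7 at SD 14.

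These sizes depend on distributions and an obesity share that the documents do not give. A low obesity share or strong skew on the raw scale would lose more; a true step at the chosen cut would lose nothing. The consequence is less precise hypothesis generation.

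**What to change.** Keep every listed cut for display. In SAP Regression models, add as exploratory analyses a treatment-by-modifier term on the continuous scale for age, BMI, baseline FiO2/SpO2, days since symptom onset and triglycerides (log scale). Fit each in the linear model already planned for continuous outcomes. Report the slope with its 95% CI and the estimated effect at the 10th, 50th and 90th percentiles of the modifier. Use a spline, or the displayed cuts, to check linearity. Report the number of patients with triglycerides measured.

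State that the slope is easiest to interpret for the day-count outcomes, and that on the global rank score it describes a difference in mean rank, not the Mann-Whitney parameter.

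The cost is a few lines of SAP text and five extra exploratory terms. No new data are needed and the primary analysis does not change. The drawback is the linearity assumption, which the check addresses.
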